4.1.2. Part 2: Participants with Atopic Dermatitis

Part 2 is a randomized, participant- and investigator-blind, sponsor-open, placebo-controlled investigation of the safety, tolerability, PK, and pharmacodynamics (including effects on clinical signs and symptoms) of PF-07242813 in adult participants with moderate to severe atopic dermatitis (AD).

In Part 2, Cohort 9 will randomize (2:1, PF-07242813) 24 participants at the MTD defined in Part 1 (or maximum dose studied in Part 1 if MTD is not achieved) for the assessment of the safety, tolerability, PK, and clinical effects of PF-07242813 in AD and **CCI** [REDACTED]. The number of participants enrolled in Cohort 9 will provide a sample size sufficient for statistical evaluation of the primary efficacy endpoint (placebo-corrected percent change from baseline in continuous EASI).

Cohort 9 will be initiated following completion of all single dose cohorts evaluated in Part 1 and review of cumulative safety and PK data from Part 1. Participants in Cohort 9 will receive the study intervention on Day 1 at the MTD identified in Part 1, or the highest dose studied in Part 1 if MTD is not achieved. The dose will be administered at the clinical site, and participants will return for outpatient visits per the [Schedule of Activities \(Table 3\)](#), up to Week 16.

An optional cohort (Cohort 16) of up to 24 moderate to severe AD participants may be enrolled as needed to evaluate further IV or SC dosing, based on cumulative safety and PK data from Part 1 and Cohort 9 in Part 2.

4.2. Scientific Rationale for Study Design

Study C4461001 represents the first time PF-07242813 will be administered to humans. Therefore, this first-in-human (FIH) study will employ an escalating dose design initially using single doses and then, once the safety and tolerability of higher single dose has been demonstrated, repeat doses. Study C4461001 will consist of 2 parts. Part 1 will be conducted in healthy participants; Part 2 will be conducted in participants with moderate to severe AD.

Human reproductive safety data are not available for PF-07242813, but there is no suspicion of human teratogenicity based on the intended pharmacology of the compound. Therefore, the use of a highly effective method of contraception is required (see [Appendix 4](#)).

4.2.1. Study Design Rationale for Part 1

As PF-07242813 is projected to have the PK profile of a typical mAb, the single dose phase of Study C4461001 will be initiated with a dose estimated to have little pharmacologic activity (see dose rationale, [Section 4.3.2](#), below) with dose escalation continuing until a maximally tolerated dose is identified or a dose of 1000 mg is achieved. The 1000 mg dose is predicted to provide >99% target coverage at maximal exposures, thereby assuring an adequate test of pharmacology in Part 2. The MAD phase of the study will be initiated once adequate safety data are available from a higher dose in the SAD phase of the study (see [Section 4.1.1](#)). Study C4461001 uses a placebo-controlled, blinded design to minimize bias which is justified in this early clinical study to provide a reference for safety and tolerability.

The dose escalation will be conducted in healthy participants (as defined by the [inclusion/exclusion criteria](#)) in order to establish the safety and tolerability of PF-07242813 prior to exposure in patient populations. Both adult male and female participants are eligible for enrolment in the study provided females are confirmed either to be of non-childbearing potential or, if of childbearing potential, to be using a nonhormonal form of highly effective contraception of low user dependency (such as an intrauterine device or surgical sterilization as stipulated in [Appendix 4: Contraceptive Guidance](#)). No barrier method of contraception (eg, condom) is warranted for male participants as the potential exposure to PF-07242813 via semen to partners of male participants is anticipated to be very low, as the calculated safety margin between the estimated maternal exposure due to seminal transfer at maximum dose/exposure proposed in human and the minimal anticipated biological effect level (MABEL) of PF-07242813 is in excess of 100-fold. Additionally, PF-07242813 does not have genotoxicity concerns. If emerging human PK in this study suggests the potential exposure of PF-07242813 to the partners of male participants via semen could exceed anticipated MABEL exposures at the highest proposed doses, male condom will be required for the following cohorts. As an additional safety measure, WOCBP will be required to have a negative pregnancy test prior to randomization and at pre-specified visits per the [Schedule of Activities](#).

Healthy Japanese participants will be enrolled in a separate cohort to provide a preliminary characterization of the safety, tolerability, and PK profile of PF-07242813, to support potential inclusion of Japanese patients in future studies.

Risks to study participants will be minimized by cautious dose escalation in an inpatient setting, with careful assessment and ongoing review of emerging safety data. Given that the overall potential risk of immunogenicity with PF-07242813 has been assessed to be moderate and that the cytokine release assay has suggested a low potential for cytokine release syndrome ([Section 2.2.1](#)), sentinel dosing will be implemented in all SAD cohorts (ie, cohorts where the dose being tested is the highest administered dose in the study to date). Sentinel dosing will involve administration of PF-07242813 or placebo to the first 2 participants randomized as 1: 1 in each SAD cohort, with observation for at least 24 hours to establish adequate safety and tolerability before dosing the remaining participants in the cohort.

Together, the implementation of sentinel dosing in SAD cohorts and the dose escalation rules ([Section 6.6.1](#)) are expected to minimize the risk to study participants while providing key safety and tolerability information. As is standard for FIH studies, dose administration will be conducted in the fasting state in order to facilitate management of any adverse events that may occur shortly after dosing.

CCI

associated safety concern at the last scheduled visits eg, Day 99 visit (~70 days after 3rd dose)
CCI [REDACTED]

[REDACTED]

Staining of neuroendocrine cells with PF-07242813 in the human anterior pituitary was observed in a tissue cross reactivity study that was not observed in the homologous cynomolgus monkey tissues ([Section 2.2.1](#)). The overall risk of pituitary toxicity in humans is considered low; however selected anterior pituitary hormones and hormones regulated by them will be monitored in SAD/MAD cohorts as a screen for potential adverse effects on the pituitary gland.

Currently, the final scheduled out-patient visits in SAD and MAD cohorts (except Cohorts 1-3 in SAD) are planned to be approximately 70 days after last dose, which is >4 times of PF-07242813 t_{1/2} predicted in human (17 days). Based on emerging data, the last out-patient visit schedule may be modified in the following cohorts to cover at least 4 half-lives of PF-07242813 observed in previous cohorts.

4.2.2. Study Design Rationale for Part 2

The objectives of Part 2 of Study C4461001 are to assess the safety and tolerability of PF-07242813 at a single maximally planned or maximally tolerated dose in participants with moderate to severe AD, and to provide preliminary data on the effects of PF-07242813 on clinical signs and symptoms of AD.

Part 2 of Study C4461001 will consist of up to 2 cohorts of participants with moderate to severe AD (Cohorts 9 and optional Cohort 16). Participants in Cohort 9 will receive a single IV dose of study intervention at the MTD established in Part 1 (or the highest dose studied in Part 1 if MTD is not achieved). The sample size of approximately 24 participants with AD in Cohort 9 will support the assessment of clinical activity for the primary efficacy endpoint. This approach is justified by the accumulated single and available multiple dose safety data generated in the healthy participants, and the extended duration of high target occupancy predicted at this dose.

The optional Part 2 cohort (Cohort 16) would allow for further investigation of the safety, tolerability, PK, and pharmacodynamics of PF-07242813 at lower or repeat doses, as deemed necessary based on emerging data. As for Part 1, Part 2 of Study C4461001 will be blinded to the site personnel (with the exception of the site pharmacist and, as needed, an individual designated to administer study intervention who is not otherwise associated with the study) and placebo-controlled, with the same rationale.

As noted above, a secondary objective of Part 2 is to evaluate the potential clinical activity of PF-07242813 in patients with moderate to severe AD in order to guide future development of the molecule. The patient population defined by the inclusion/exclusion criteria, the predicted human PK profile, and the resultant predicted level and duration of target engagement is expected to provide an adequate test of the pharmacology of PF-07242813 in inhibiting CD1a proinflammatory signaling in AD. The sample size and randomization schemes is expected to be sufficient to detect clinically meaningful improvement in AD signs and symptoms (see [Section 9.2.2](#)).

Women of childbearing potential (WOCBP) will be eligible for participation if they agree and adhere to the contraception guidelines stipulated in this protocol ([Appendix 4: Contraceptive](#)), which include hormonally based contraception methods. Although reproductive safety data are not available for PF-07242813, there is no suspicion of human teratogenicity, genotoxicity, or clastogenicity based on the pharmacology of the compound that would preclude the inclusion of WOCBP using highly effective contraception into a controlled clinical trial. Compared to the contraception requirements in Part 1, the allowance for hormonal methods of contraception is justified by the accumulated safety and tolerability data from the SAD and MAD cohorts in Part 1 and will facilitate recruitment given that many patients with AD are of reproductive age and capacity. As an additional safety measure, WOCBP will be required to have a negative pregnancy test prior to randomization and at all study visits.

For both **Part 1 and Part 2**, Banked Biospecimens will be collected and stored for further analyses which may, for example, provide greater understanding of the study intervention.

4.3. Justification for Dose

4.3.1. Prediction of Human PK and Efficacious dose

Based on the serum PK parameter values observed for PF-07242813 in nonclinical species, the predicted 2-compartment PK parameter values in humans are expected to be the same as those of a typical therapeutic IgG mAb. These values have been reported previously (Dirks and Meibohm 2010; Betts et al. 2018)^{8,2} and were used for the PF-07242813 human PK predictions as follows: 3.2 L for central volume, 2.2 L for peripheral volume, 0.25 L/day for central CL, 0.45 L/day for distributive clearance, 0.26 1/day for SC absorption rate constant and 60% for SC bioavailability. The predicted volume and clearance values resulted in a 17-day $t_{1/2}$ and a 5.4 L V_{ss} .

As there are no validated mechanism-based biomarkers or preclinical disease/efficacy model for human AD, the efficacious dose of PF-07242813 has been projected empirically, as a dose that will achieve >95% CD1a receptor occupancy at steady state trough concentrations at the site of action (skin). A site of action model was used to link PF-07242813 exposure to CD1a receptor occupancy using the PF-07242813 K_D and the predicted human PK parameters, CD1a concentrations in skin and CD1a internalization/turnover rate. Using this approach, the predicted efficacious human dose of PF-07242813 is estimated to be 30 mg SC q4wk. The projected steady state AUC_{tau} ($\tau=4$ weeks/672 hrs), C_{ave} and C_{max} associated with the predicted efficacious dose are 1730 $\mu\text{g.h/mL}$, 2.58 $\mu\text{g/mL}$ and 3.67 $\mu\text{g/mL}$.

4.3.2. Dose Rationale for Part 1

The nonclinical safety profile of PF-07242813 has been adequately characterized to support development into human clinical studies of up to 3 months in duration. No test article-related effects or target organs were identified following once weekly administration of PF-07242813 in a pivotal 13-week cynomolgus monkey toxicity study with the NOAEL defined as the highest dose tested, 200 mg/kg/week (IV). In this study, the C_{max} and AUC_{168H} exposure limit for dose escalation are set to be 1020 μ g/mL and 106000 μ g/mL, respectively, determined as 1/10th of the mean exposures observed at NOAEL in the monkey toxicity study.

A starting dose of 0.3 mg PF-07242813 IV is planned. The predicted PF-07242813 C_{max} and AUC_{168H} at the 0.3 mg single dose are approximately 10890-fold and 11150-fold, respectively, below the exposure limits pre-defined for PF-07242813 dose escalation (see Table 4). The predicted exposures at the 0.3 mg single dose are approximately 39- and 82-fold below the steady-state exposure at projected efficacious dose (30 mg SC Q4W) for C_{max} and AUC_{tau} ($\tau=4$ weeks/672 hrs), respectively. The maximum CD1a receptor occupancy at skin, the site of action after 0.3 mg IV single dose is predicted to ~29%, at which level little pharmacological effect is expected as PF-07242813 is an antagonist of CD1a target engagement. The starting dose selection is consistent with the EMA guideline on first-in-human study (EMA Guideline on strategies to identify and mitigate risks for first-in-human and early clinical trials with investigational medicinal products) and a recent white paper on FIH starting dose selection by the IQ consortium (Leach et al. 2020).¹⁴ The highest proposed IV infusion dose of 1000 mg is estimated to provide an exposure margin of 3.3-fold for both C_{max} and AUC_{168H} , relative to the exposure limits.

Table 4. Projected Exposures, Maximum CD1a Receptor Occupancy and Safety Margins Following Single IV Doses of PF-07242813^a

DOSE (mg)	C_{max} (μ g/mL)	AUC_{168H} (μ g·h/mL)	$SM_C_{max}^b$ (fold)	SM_AUC^b (fold)	RO ^c (%)
0.3	0.09368	9.51	10890	11150	29.3
1	0.3111	31.65	3279	3349	59.2
3	0.9332	94.95	1093	1116	81.2
10	3.111	316.5	328	335	93.8
30	9.332	949.5	109	112	97.9
100	31.11	3165	33	33	99.4
300	93.32	9495	11	11	99.8
1000	311.1	31650	3.3	3.3	99.9

a. Human PK was predicted using 2-CM model with IV infusion and linear PK. For dose <1 mg, infusion over 10 min, otherwise, infusion over 1 hour. $V_c=3.2$ L, $V_p=2.2$ L, $CL=0.25$ L/day, $Q=0.45$ L/day. For dose <1 mg, it is assumed that infusion over 10 min, otherwise, infusion over 1 hour.

b. SM= safety margin, which is calculated relative the exposure limit ($C_{max} = 1020 \mu$ g/mL and $AUC_{168H}=106000 \mu$ g·h/mL), determined as 1/10th of the mean exposure at NOAEL of 200 mg/kg/week IV in pivotal 13-week cynomolgus monkey toxicity study.

c. A site of action model was used to predict CD1a receptor occupancy at skin with the predicted human PK.

The dose range of 15 mg to 300 mg SC administered every two weeks (Q2W) in total of 3 doses were selected for dose escalation in 4 MAD cohorts (Table 5). The dosing regimen of every two weeks (Q2W) was selected to achieve high exposures of PF-07242813 with fewer doses compared to monthly dosing for adequate safety assessment. The multiple dose period is planned to be initiated at the 15 mg SC dose level with the C_{max} and AUC_{168H} following 3 repeated doses, each dose predicted to be 424- and 287-fold below the exposure limits pre-defined. The predicted exposures following 3 repeated doses at 15 mg SC are also below the steady-state exposures at projected efficacious dose (30 mg SC Q4W) for both C_{max} (2.405 vs 3.67 μ g/mL) and AUC_{tau} (1144 vs 1730 μ g.h/mL over 4 weeks/672 hrs). At the highest dose proposed (1000 mg IV) in an optional MAD cohort, the predicted margins for C_{max} and AUC_{168H} , relative to the exposure limits, are 2.3- and 2.1-fold, respectively (Table 5).

Table 5. Projected Exposures, Maximum CD1a RO and Safety Margins After the 3rd Dose of Multiple SC or IV Doses of PF-07242813^a

DOSE (mg q2wk) ^b	C_{max} (μ g/mL)	T_{max} (hr)	AUC_{168H} (μ g·hr/mL)	C_{ave}^c (μ g/mL)	SM_ C_{max}^d (fold)	SM_ AUC^d (fold)	SM_ C_{ave}^d (fold)	Max RO ^e (%)
15	2.405	96	369.4	2.092	424	287	302	96.3
50	8.017	96	1231	6.973	127	86	91	98.7
150	24.05	96	3694	20.92	42	29	30	99.6
300	48.1	96	7388	41.84	21	14	15	99.8
1000 IV	441.6	1	50640	245	2.3	2.1	2.6	99.9

- a. Human PK was predicted using 2-CM model with S.C. in which $V_c=3.2$ L, $V_p=2.2$ L, $CL=0.25$ L/day, $Q=0.45$ L/day, 0.26 1/day for SC absorption rate constant and 60% for bioavailability were used. PK parameters after the 3rd dose are presented.
- b. Dose is given q2wk with 3 doses in total. All the doses are given as subcutaneously except 1000 mg which is given IV over 1 hr infusion.
- c. $C_{ave}=AUC_{tau}/336$ ($\tau=336$ hours for q2wk dosing in MAD cohorts).
- d. SM=safety margin, which is calculated relative the exposure limits of $C_{max}=1020$ μ g/mL and $AUC_{168H}=106000$ μ g.h/mL, determined as 1/10th of the mean exposure at NOAEL of 200 mg/kg/week IV in pivotal 13-week cynomolgus monkey toxicity study. C_{ave} used for safety margin calculation is exposure limit of AUC_{168H} divided by 168 hr.
- e. A site of action model was used to predict CD1a receptor occupancy at skin with the predicted human PK.

4.3.3. Dose Rationale for Part 2

A single dose of study intervention is planned in 24 adult participants with AD (Cohort 9), at the maximum tolerated dose (MTD) observed in Part 1 or the highest dose studied in Part 1 if MTD is not achieved (eg, the planned maximum dose of 1000 mg). Following a 1000 mg single IV dose of PF-07242813, the predicted CD1a receptor occupancy would be saturated and remain high (>95%) for greater than 16 weeks. An optional cohort (Cohort 16) may be used to evaluate further IV or SC dosing of PF-07242813, based on cumulative safety and PK data from Part 1 and Cohort 9 in Part 2.

4.4. End of Study Definition

A participant is considered to have completed the study if he/she has completed all phases of the study, including the End-of-Study visit.

The end of the study is defined as the date of the last visit of the last participant in the study.

5. STUDY POPULATION

This study can fulfill its objectives only if appropriate participants are enrolled. The following eligibility criteria are designed to select participants for whom participation in the study is considered appropriate. All relevant medical and nonmedical conditions should be taken into consideration when deciding whether a particular participant is suitable for this protocol.

Prospective approval of protocol deviations to recruitment and enrollment criteria, also known as protocol waivers or exemptions, is not permitted.

5.1. Inclusion Criteria

Participants are eligible to be included in the study only if all of the following criteria apply:

Age and Sex:

1. **Part 1 only:** Adult male or female participants between 18 to 55 years of age, inclusive, at the time of signing the ICD.
 - Refer to [Appendix 4](#) for reproductive criteria for males ([Section 10.4.1](#)), females of non-child bearing potential ([Section 10.4.2](#)), and females of child-bearing potential ([Section 10.4.3](#)).

OR

Part 2 only: Male or female participants, who at the time of screening, are between the ages of 18 and 65 years, inclusive.

- Refer to [Appendix 4](#) for reproductive criteria for male participants ([Section 10.4.1](#)), females of non-child bearing potential ([Section 10.4.2](#)), and females of child-bearing potential ([Section 10.4.3](#)).

Type of Participant and Disease Characteristics:

2. Participants who are willing and able to comply with all scheduled visits, treatment plan, laboratory tests, and other study procedures.
3. **Part 1 only:** Participants who are overtly healthy as determined by medical evaluation including medical history, physical examination, vital sign assessments, temperature, 12-lead ECGs, laboratory tests.

4. **Part 1, Japanese cohort:** Healthy adults of Japanese descent, where parents and grandparents are Japanese.
5. **Part 2 only:** Must meet the following atopic dermatitis criteria:
 - a. Have a clinical diagnosis of chronic atopic dermatitis (also known as atopic eczema) for approximately 1 year prior to Day 1 and have the diagnosis of AD confirmed (Hanifin and Rajka criteria of AD).¹⁰
 - b. Either have had an inadequate response to treatment with topical medications (for at least 4 consecutive weeks within 1 year of the first dose of the study drug).

OR

Have a documented reason why topical treatments are considered medically inappropriate (eg, because of important side effects or safety risks) within the last year.

- c. Have moderate to severe AD (defined as having an affected BSA (captured as part of EASI) $\geq 10\%$, IGA ≥ 3 , and EASI ≥ 12 at both the screening and baseline visits).
- d. Have an otherwise healthy medical evaluation (other than signs and symptoms of AD) including medical history, physical examination, vital sign assessments, temperature, 12-lead ECGs, laboratory tests.

Note: Controlled comorbid diseases (ie, controlled diabetes not requiring insulin, controlled hypertension), are acceptable, so long as they do not require administration of prohibited medications.

- e. Mild or moderate asthma that is well-controlled (not requiring high dose inhaled corticosteroids, systemic [oral or parenteral] corticosteroids, or biologic asthma treatments).

Weight:

6. **Part 1:** BMI of 17.5 to 30.5 kg/m²; and a total body weight >50 kg (110 lbs);
Part 2: BMI of 17.5 to 40 kg/m²; and a total body weight >50 kg (110 lbs).

Informed Consent:

7. Capable of giving signed informed consent as described in [Appendix 1](#), which includes compliance with the requirements and restrictions listed in the ICD and in this protocol.

5.2. Exclusion Criteria

Participants are excluded from the study if any of the following criteria apply:

Medical Conditions:

1. Evidence of active, latent, or inadequately treated infection with Mycobacterium tuberculosis (TB) as defined by both of the following:
 - a. A positive QuantiFERON-TB Gold In-tube or equivalent test.
 - b. History of either untreated or inadequately treated latent or active TB infection, or current treatment for the same.
2. History of HIV infection, hepatitis B, or hepatitis C; positive testing for HIV, hepatitis B surface antigen (HBsAg), hepatitis B core antibody (HBcAb) or hepatitis C antibody (HCVAb). Hepatitis B vaccination is allowed. As an exception a positive HBsAb test due to hepatitis B vaccination is permissible.

Testing for SARS-CoV-2 will be at the discretion of the investigator, based on local infection rates, patient exposure history, and reported signs or symptoms of COVID-19.

3. Other medical or psychiatric condition including recent (within the past year) or active suicidal ideation/behavior or laboratory abnormality that may increase the risk of study participation or, in the investigator's judgment, make the participant inappropriate for the study.
 - *Part 2 only:* At Screening Visit, if there are "yes" answers on items 4, 5 in the past year or on any question in the suicidal behavior section of the Columbia-Suicide Severity Rating Scale (C-SSRS) in the past 6 months, the participant will not be included in the study.
4. Known history of or evidence of current endocrine disease.
5. Have a history of systemic infection requiring hospitalization, parenteral antimicrobial therapy, or as otherwise judged clinically significant by the investigator within 6 months prior to Day 1.
6. Recent exposure to live or attenuated vaccines within 28 days of the screening visit.
7. Have any malignancies or have a history of malignancies with the exception of adequately treated or excised non-metastatic basal cell or squamous cell cancer of the skin, or cervical carcinoma in situ.

8. Have a history of any lymphoproliferative disorder such as Epstein Barr Virus (EBV) related lymphoproliferative disorder, history of lymphoma, leukemia, or signs and symptoms suggestive of current lymphatic or lymphoid tissue disease.
9. Evidence or history of clinically significant hematological, renal, endocrine, pulmonary, gastrointestinal, cardiovascular, hepatic, psychiatric, neurological, immunological/rheumatological.
10. **Part 1 only:** allergic disease (including drug allergies, but excluding untreated, asymptomatic, seasonal allergies at the time of dosing).

Additional Exclusionary Medical Criteria for Part 2 (Atopic Dermatitis Cohorts)

11. **Part 2:** Currently have active forms of other inflammatory skin diseases.
12. **Part 2:** Have history of or current evidence of skin conditions (eg, psoriasis, seborrheic dermatitis, lupus) at the time of Day 1 that would interfere with evaluation of atopic dermatitis or response to treatment.
13. **Part 2:** Have active chronic or acute skin infection requiring treatment with systemic antibiotics, antivirals, antiparasitics, antiprotozoals, or antifungals within 2 weeks prior to Day 1, or superficial skin infections within 1 week prior to Day 1.
NOTE: potential participants may be rescreened after infection resolves.
14. **Part 2:** Score of >5 on the Fitzpatrick Skin Type Assessment.
15. **Part 2:** History of anaphylaxis with the following exceptions: participants with sensitivity and/or anaphylaxis only to a single, avoidable allergen (eg, aspirin, penicillin, sulfadrugs, nonsteroidal anti-inflammatory drugs [NSAIDs], peanuts) may be enrolled, if in the opinion of the investigator, the participant is aware of the hypersensitivity and avoids -the problematic allergen. Participants must carry appropriate treatment for anaphylaxis and must know how to manage anaphylactic reactions.

Prior/Concomitant Therapy:

16. Participation in any other cohort of this study: participants can only be randomized once into this study and be assigned to 1 cohort only.
17. Have undergone significant trauma or major surgery within 1 month of the first dose of study drug.
18. **Part 1 only:** Use of prescription or nonprescription drugs and dietary and herbal supplements within 7 days or 5 half-lives-(whichever is longer) prior to the first dose of PF-07242813. (Refer to [Section 6.5.1](#) for additional details).

19. **Part 2 only:** Have received any of the treatment regimens within the specified timeframes as outlined in [Section 6.5.2.2](#) (Prohibited Treatments and Medications During the Study).

Prior/Concurrent Clinical Study Experience:

20. Treatment with an investigational drug within 28 days (or as determined by the local requirement) or 5 half-lives preceding the first dose of study treatment (whichever is longer).
21. **Part 2 only:** Any investigational or experimental therapy taken or procedure performed for AD, psoriasis, psoriatic arthritis, rheumatoid arthritis or other inflammatory diseases in the previous 1 year should be discussed with the Pfizer Medical Monitor (or designee).

Diagnostic Assessments:

22. A positive urine drug test (please refer to [Section 10.2](#)).
23. **Part 1:** Screening supine blood pressure ≥ 140 mm Hg (systolic) or ≥ 90 mm Hg (diastolic) 1 for healthy adults.
Part 2: Screening supine blood pressure ≥ 160 mm Hg (systolic) or ≥ 100 mm Hg (diastolic), following at least 5 minutes of supine rest.

For Part 1 and Part 2, if blood pressure (BP) meets the criteria above for a given single measurement, the BP should be repeated two more times and the average of the three BP values should be used to determine the participant's eligibility.

24. Baseline 12-lead ECG that demonstrates clinically relevant abnormalities that may affect participant safety or interpretation of study results (eg, baseline QTc interval >450 msec, complete LBBB, signs of an acute or indeterminate-age myocardial infarction, ST-T interval changes suggestive of myocardial ischemia, second- or third-degree AV block, or serious bradyarrhythmias or tachyarrhythmias). If the baseline uncorrected QT interval is >450 msec, this interval should be rate-corrected using the Fridericia method and the resulting QTcF should be used for decision making and reporting. If QTc exceeds 450 msec, or QRS exceeds 120 msec, the ECG should be repeated 2 more times and the average of the 3 QTc or QRS values should be used to determine the participant's eligibility. Computer-interpreted ECGs should be overread by a physician experienced in reading ECGs before excluding participants.

25. Participants with **ANY** of the following abnormalities in clinical laboratory tests at screening, as assessed by the study-specific laboratory and confirmed by a single repeat test, if deemed necessary:

- a. **Part 1:** AST **or** ALT level $>1.2 \times \text{ULN}$;
Part 2: AST **or** ALT level $\geq 3 \times \text{ULN}$
- b. Total bilirubin level $\geq 1.5 \times \text{ULN}$; participants with a history of Gilbert's syndrome may have direct bilirubin measured and would be eligible for this study provided the direct bilirubin level is $\leq \text{ULN}$.
- c. History or current evidence of anterior pituitary disorders Screening test results
CCI
[REDACTED]

Other Exclusions:

26. History of alcohol abuse or binge drinking and/or any other illicit drug use or dependence within 6 months of Screening. Binge drinking is defined as a pattern of 5 (male) or 4 (female), or more alcoholic drinks in about 2 hours. As a general rule, alcohol intake should not exceed 14 units per week (1 unit = 8 ounces (240 mL) beer, 1 ounce (30 mL) of 40% spirit or 3 ounces (90 mL) of wine).
27. Blood donation (excluding plasma donations) of approximately 1 pint (500 mL) or more within 60 days prior to dosing.
28. History of sensitivity to heparin or heparin-induced thrombocytopenia.
29. Unwilling or unable to comply with the criteria in the **Lifestyle Considerations** section of this protocol.
30. Investigator site staff or Pfizer employees directly involved in the conduct of the study, site staff otherwise supervised by the investigator, and their respective family members.
31. Pregnant female participants, breastfeeding female participants, male participants with partners currently pregnant, or male or female participants pursuing artificial reproductive technologies including but not limited to sperm/egg donation (see **Section 5.3**).
32. Use of tobacco/nicotine containing products more than 5 cigarettes/day.

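### Exclusion criterion 1 requires a positive TB test and a TB history together, so it does not exclude a test-negative person with untreated, inadequately treated or currently treated TB

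*Protocol*

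**What the plan says.** Protocol Section 5.2 excludes a person if any one of its criteria applies. Criterion 1 covers "Evidence of active, latent, or inadequately treated infection with Mycobacterium tuberculosis (TB) as defined by both of the following". Its two items are:

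- (a) a positive result on the QuantiFERON assay or one equivalent to it;
- (b) a TB history, worded as "History of either untreated or inadequately treated latent or active TB infection, or current treatment for the same".

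The schedules of activities in Section 1.2 (Tables 1, 2 and 3) each place a QuantiFERON test at screening. No other visible section of the protocol restates the TB rule. SAP Section 2.1.2 defines the estimand population by reference to the eligibility criteria and adds nothing on TB.

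Criterion 2, directly below, is built differently for viral infections. A history excludes, and so does "positive testing for HIV, hepatitis B surface antigen (HBsAg), hepatitis B core antibody (HBcAb) or hepatitis C antibody (HCVAb"). It then states an exception for antibody due to hepatitis B vaccination.

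**The concern.** The heading of criterion 1 names active, latent and inadequately treated infection. Its definition is narrower, because it joins a test result and a history with an AND. A history of inadequately treated TB, or TB treatment in progress, does not trigger the rule unless the QuantiFERON is also positive.

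What is at stake is whether a stated safety exclusion does what it says. If the one TB rule does not apply, the decision passes to general criteria that do not name TB, or to how the site reads item (b). Protocol Section 4.3.3 predicts receptor occupancy above 95% for more than 16 weeks after a single 1000 mg IV dose, so an eligibility error at that dose could not be undone by stopping treatment.

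**Working it through.** No figure in the plan bears on this point, so the check is one of logic. Criterion 1 as written is met only if (a) AND (b) are both true. Item (b) can be read in two ways for TB first found at screening: literally, where it needs an earlier TB history, or broadly, where a new finding counts as untreated infection. The last column applies the wording proposed under the fix.

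| Case | (a) | (b) literal / broad | As written: literal / broad | Proposed wording |
|---|---|---|---|---|
| Negative test, untreated or inadequately treated history | no | yes / yes | not excluded / not excluded | excluded by (b) |
| Negative test, current TB treatment | no | yes / yes | not excluded / not excluded | excluded by (b) |
| Positive test, no earlier TB history | yes | no / yes | not excluded / excluded | excluded by (a) |
| Positive test, untreated or inadequately treated history | yes | yes / yes | excluded / excluded | excluded by (a) and (b) |
| Negative test, no earlier history, active TB evident at screening | no | no / yes | not excluded / not excluded | excluded by (c) |
| Positive test, adequately treated history, no active disease | yes | no / no | eligible / eligible | eligible by the exception |

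Three things follow.

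1. Every test-negative row escapes criterion 1 on both readings, because item (a) fails. Only reading both as either would change this, and nothing in the text supports that.
2. The positive test without a history changes outcome with the reading of (b). That is an ambiguity rather than a certain gap.
3. Changing both to either, with no other edit, would still miss active TB found at screening with a negative test and no earlier history if (b) is read literally. It would also exclude the last row. A third item and an exception are therefore both needed.

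The other provisions that could catch a test-negative person are:

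| Provision | What it can catch | Limit |
|---|---|---|
| Section 5, introduction | Any relevant medical condition, when judging suitability | General; no TB rule |
| Criterion 3 | A condition or "laboratory abnormality that may increase the risk of study participation" | Depends on a risk assessment or investigator judgment |
| Criterion 5 | A "history of systemic infection requiring hospitalization, parenteral antimicrobial therapy, or as otherwise judged clinically significant by the investigator" | Only the 6 months before Day 1 |
| Criterion 9 | "Evidence or history of clinically significant hematological, renal, endocrine, pulmonary, gastrointestinal, cardiovascular, hepatic" and other disease | Must be clinically significant; latent infection without symptoms need not be |
| Inclusion 3 (Part 1) | Anyone not overtly healthy on evaluation | Past TB in a well person is not clearly covered |
| Inclusion 5d (Part 2) | Anyone who does not "Have an otherwise healthy medical evaluation (other than signs and symptoms of AD") | Same limit for past TB |
| Criterion 18 (Part 1) | Current TB drugs, firmly | Part 1 only |

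For current treatment in Part 2, the note to inclusion 5d matters: "Controlled comorbid diseases (ie, controlled diabetes not requiring insulin, controlled hypertension), are acceptable". The note uses ie, so it can be read as a closed list on which TB does not appear. Against that, Section 6.5.2.2 does not name TB drugs as prohibited, and Section 6.5.2.1 allows other necessary medication that is not prohibited.

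**The case against.** The strongest reply has four parts.

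**The conjunction has a purpose.** It keeps people with adequately treated past TB eligible when their test stays positive. This stands, and the fix must preserve it. It does not require the AND, since an exception does the same work, as criterion 2 shows for vaccination.

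**The general provisions already cover the ground.** This stands in part. Criterion 18 firmly excludes current TB drugs in Part 1. In Part 2, inclusion 5d is mandatory and its note, read as a closed list, leaves TB under treatment outside the accepted comorbidities. A reader might infer that people on TB treatment could simply enter Part 2; the documents do not support that. What is left is narrower: a negative test, past untreated or inadequately treated TB, and an otherwise healthy evaluation.

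**A positive test without treatment is naturally untreated latent TB.** This is a fair reading of (b). A reader might infer that newly found latent TB is certain to pass criterion 1; the text supports only the statement that the outcome depends on how (b) is read.

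**The clinical importance is not shown.** This stands. Protocol Section 2.2 describes a mechanism distinct from broadly immunosuppressive treatment. No visible section names TB reactivation, and the risk table in Section 2.3.1 is redacted, so the sponsor's assessment cannot be seen.

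**Conclusion.** Criterion 1 is wrong as written, and this is a minor correction to a safety rule. The negative-test gap is certain on the text, given the ordinary meaning of both. The newly found latent case is an ambiguity. Active TB first evident at screening with a negative test also falls outside criterion 1, although its heading covers it; general criteria would be expected to act there.

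The size cannot be stated. The documents give no TB prevalence among people screened, and planned randomized numbers would not measure how often the gap matters. A reader might infer that the trial would knowingly enroll people with TB, or that the drug carries a known reactivation risk. Neither follows: the general provisions reduce the gap considerably, and nothing visible describes such a risk. Endpoints, power and analysis do not depend on this point.

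**What to change.** Amend Protocol Section 5.2, criterion 1, as follows:

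- Replace the word both in the lead-in with any.
- Keep items (a) and (b) unchanged.
- Add *(c) current clinical evidence of active TB.*
- Add *Exception to (a): a positive test in a participant with documented adequate treatment of prior latent or active TB and no current evidence of active disease.*

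This makes the definition match its heading, settles the newly found latent case, and keeps adequately treated people with a persistently positive test eligible. The cost is a short amendment and slightly more screen failures. No sample size, endpoint or analysis text changes.
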